6.5. Pooling of Centres

Not applicable.

6.6. Subgroups

The primary, secondary, explorative and safety endpoints will be also summarized within each stratification subgroup (absence/presence of Primary Sjögren's Syndrome).

In order to assess the impact of COVID-19 on primary efficacy endpoint and on safety, subgroup analyses will be performed (affected patients versus non affected patients) if 10% or more treated subjects are affected by COVID-19 during the study.

This document is confidential.

7. Demographic, Other Baseline Characteristics and Medication

Demographics and others baseline characteristics are presented in tables 14.1 to 14.1.3.1 (see section15)

7.1. Patient Disposition and Withdrawals

The following frequencies (number and percent) will be displayed in the patient disposition table, by treatment group and overall:

- Number of patients enrolled;
- Number of patients screen failure;
- Number of patients randomized (overall and by strata);
- Number (%) of patients in the FAS (Full Analysis Set) (overall and by strata);
- Number (%) of patients in the PP set (overall and by strata);
- Number (%) of patients in the Safety Set (overall and by strata);
- Number (%) of patients who completed the study (overall and by strata);
- Number (%) of patients who discontinued the study early and reasons for discontinuation (overall and by strata).

The disposition analyses will be based on the Enrolled Set.

The denominators for the percent calculations will be the number of patients in the randomized set or in the specific analysis set.

Patient completion status, date of completion/discontinuation and reason for discontinuation will be listed.

7.2. Demographic and Other Baseline Characteristics

The following baseline and demographic characteristics will be summarized per treatment group and overall:

- Age (years). Age is recorded directly in the database and is not calculated separately
- Gender (Male, Female)
- Race (American Indian or Alaska Native; Asian; Black or African American; Native Hawaiian or Other Pacific Islander; White or Caucasian; Other)
- Ethnicity (Hispanic, Latino or Spanish; Not Hispanic, Latino or Spanish)
- Eligible eye (Right, Left)
- Time since diagnosis of dry eye

Demographic and background data will be summarized using summary statistics, as appropriate.

The Full Analysis Set will be used to present these data.

In case there is a relevant difference ($\geq 10\%$) in sample size among the different datasets (Randomized, SAF, FAS and PP), these data will be also presented using other sets.

This document is confidential.

7.3. Ocular and Systemic Medical History and Concomitant Diseases

Ocular and Systemic Medical History and Concomitant Diseases are presented in tables 14.1.3.2.1 to 14.1.3.2.2 (see section15).

Ocular and systemic medical history will be coded to system organ class (SOC) and preferred term (PT) using Medical Dictionary for Regulatory Activities (MedDRA) version 21.1.

Tables for ocular medical history and systemic medical history will be provided using the Safety Set.

Data will be summarized, by SOC and PT and sorted alphabetically. Conditions that are reported more than once for a given SOC and PT will be counted only once per patient on the PT level for each SOC.

The Safety Set will be used to present these data.

A corresponding data listing will be presented for all enrolled patients.

7.4. Medication

Medications are presented in tables 14.1.4.1.1 to 14.1.4.2.2 (see section15).

Prior and concomitant medications will be coded by the Anatomical Therapeutic Chemical (ATC) classification system according to the World Health Organization Drug Dictionary (WHODRUG), WHODrugDDEB2 - 201901.

A listing of prior and concomitant medications will be provided for all enrolled patients (prior medications) and randomized patients (concomitant medications).

7.4.1. Previous Ocular and Systemic Medication

Previous ocular and systemic medications are defined as those medications recorded on the Previous Ocular and Systemic Medications pages of the eCRF.

Tables for previous ocular medication and previous systemic medication will be provided using the Safety set.

For the summary tables, the count and percentage of patients under each ATC class level 2 and Preferred name will be summarized by treatment group.

If a patient has taken prior medications more than once, the patient will be counted only once under any given drug class.

7.4.2. Concomitant Ocular and Systemic Medication

Concomitant ocular and systemic medications are defined as those medications recorded on the Concomitant Ocular and Systemic Medications pages of the eCRF.

Tables for concomitant ocular medication and concomitant systemic medication will be provided using the Safety Set.

For the summary tables, the count and percentage of patients under each ATC class level 2 and Preferred name will be summarized by treatment group.

If a patient has taken concomitant medications more than once, the patient will be counted only once under any given drug class.

This document is confidential.

8. Efficacy

For the purpose of efficacy analysis in this trial, the statistical analysis (both descriptive and inferential) will be done on the eligible eye when applicable.

Results from both eyes will be presented in the listings.

Primary and secondary efficacy endpoints will be summarized using the FAS and Per Protocol set. Efficacy endpoints will be also summarized for patients with the Primary Sjögren's syndrome and for patients without the Primary Sjögren's syndrome .

Efficacy are presented in tables 14.2.1.1.1 to 14.2.2.15.2.3 (see section15)

8.1. Primary Efficacy Endpoint and Analysis

The primary efficacy endpoint is the change from baseline in Schirmer test I (without anesthesia) versus Week 4. The primary analysis is based on the FAS population. Missing data will be replaced by means of the Last Observation Carried Forward (LOCF) method.

The Schirmer test I will be summarized using descriptive statistics for continuous variables by treatment and visit. The change from baseline value will also be summarized for all post-baseline visits. The same summary analysis will be provided after pooling the treated patients (20 µg/mL BID arm and 20 µg/mL TID) together. Comparison (descriptive in nature) of the change from baseline of each treatment versus placebo will be performed by means of a t-test at each timepoint.

The primary analysis will be performed by means of an analysis of variance including only treatment as main factor followed by pre-planned comparisons from Vehicle and rhNGF dosages according to Williams' procedure.

The first comparison will compare the rhNGF TID dose to the Placebo using Williams test.

In case of significant result then the rhNGF BID dose will be compared to the Placebo; if the result is not significant then the test will be stopped.

Description of the Williams' Test:

μ_0 = Effect of Placebo

μ_1 = Effect of rhNGF BID

μ_2 = Effect of rhNGF TID

Hypotheses:

$H_0: \mu_0 = \mu_1 = \mu_2$

$H_1: \mu_0 <= \mu_1 \leq \mu_2$

The test develops into two phases:

* First step

Starting from the observed means X_i , determine the maximum likelihood estimates M_i (corrected mean of group i after amalgamation) under the alternative hypothesis.

If X_i satisfies the inequalities written in H_1 then $M_i = X_i$

Otherwise pool any adjacent violators into the same value:

$M_i = (n_i * X_i + n_{i+1} * X_{i+1}) / (n_i + n_{i+1})$ where n_i = sample size of group i.

The process is repeated until the means are completely ordered.

This document is confidential.

*** Second step**

Calculate the test statistic given by
 $T_k = (M_k - X_0) / s * \sqrt{1/n_0 + 1/n_k}$

where s = root mean square error and X_0 is the observed mean in the placebo group.

The fact that the k th dose level is the minimum effective dose is concluded if $T_j > t_{j,\alpha}$ for all $j \geq k$ where the $t_{j,\alpha}$ values are the critical values reported by Williams [2].

The Schirmer test I values will be also listed.

An explorative sensitivity analysis of the primary endpoint will be conducted including in the analysis of variance the absence/presence of diagnosis of Primary Sjögren's Syndrome and its interaction with treatments as covariates. If the interaction term is statistically significant (at the 0.10 level given its explorative nature), the treatment effects within patients with and without Primary Sjögren's Syndrome will be provided.

For patients already enrolled in the study, the assignment to a strata will be based on Medical history form.

If "Primary Sjogren" is recorded in the Medical condition of the Medical history form then the patient will be assigned to "Presence of Primary Sjogren"; if only "Sjogren" is recorded then the patient will be assigned to "Absence of Primary Sjogren". In all other cases, the patient will be assigned to "Absence of Primary Sjogren".

In order to assess the robustness of results of primary analysis, the Schirmer test I will be also evaluated by means of non parametric Fisher's exact test after applying the following categorization at week 4:

- A patient is defined as "Responder" if the Schirmer test I value at week 4 is greater than 10 mm/5 minutes;
- A patient is defined as "Non responder" if the Schirmer test I value at week 4 is lower or equal than 10 mm/5 minutes.

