#### 9.1. SAMPLE SIZE

In order to evaluate the minimal effective daily dose of rhNGF eye drops, a Williams design has been chosen [15; 16]. For this study three treatment groups has been considered: rhNGF eye drops solution 20  $\mu$ g/ml TID; rhNGF eye drops solution 20  $\mu$ g/ml BID plus vehicle eye drop solution SID; vehicle eye drop solution TID.

To this purpose, the sample size has been determined applying the formula eported in the publication Chow et al., 2008 at page 301 [17].

The sample size calculation for the primary variable is based on the following assumptions:

- The probability level ( $\alpha$ ) for one-sided test is set at 0.025 (see table 12.1.2 at page 298 in Chow et al., 2008) and the power level at approximately 90%.
- DELTA, in change from baseline between treatments, of 5.3 and Standard Deviation for DELTA of 10.78. Both DELTA parameters are derived from results of co-variance analysis obtained from study NGF0216 in the subset of hyposecretive patients (i.e. excluding "evaporative-only" patients).

According to this calculation, 87 patients per treatment group (for a total of 261 patients) are adequate to observe the planned difference assumed for the minimum effective daily dose. Assuming a drop-out of  $\sim$ 15%, a total of 300 is the target number of patients proposed to be enrolled.

The inclusion of at least 60 subjects with documented diagnosis of Primary Sjögren's Syndrome within the planned 300 patients will have no impact on the initial study assumptions (Standard Deviation of 10.78 and DELTA of 5.3 mm) because the patients could have been enrolled based on the previous criteria on which sample size was based. Moreover, a similar prevalence of patients with Primary Sjögren's Syndrome has already been reported in the NGF0216 medical history (~25% of patient the FAS population).

Version No. 2.0 – Final 08/AUG/2019

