The study stopped to 261 patients instead of 300 originally planned; last subject enrolled was on March 25th, 2020. On March 9th, 2020 256 patients were randomized. Among them 185 had completed the study and 44 were early terminated subjects. So only 27 subjects are ongoing and 5 not randomized at the time of national emergency due to COVID-19.

Patients affected by COVID-19 will be identified using through Adverse form and Meddra coding (Preferred Term = 'Coronavirus infection').

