9. (New criteria added in protocol version 2.0) Primary Sjögren's Syndrome Patients: patients with a documented diagnosis of Primary Sjögren's Syndrome according the American-European Consensus Group Sjögren's Syndrome Criteria (Appendix 3 of the study protocol; must meet either 4 out of 6 total criteria OR 3 out of 4 signs). Note: Subjects who are on systemic (oral) therapy for the treatment of Sjögren's Syndrome must be on stable systemic treatment defined as the same treatment for the immediately prior 90 days.

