3.5. Treatment Assignment & Masking

Eligible patients will be randomized in a 1:1:1 ratio to either rhNGF eye drops solution 20 µg/mL TID (100 patients) or rhNGF eye drops solution 20 µg/mL BID plus vehicle eye drop solution SID (100 patients) or vehicle eye drop solution TID (100 patients).

Following amendment n° 1 to the protocol, randomization will be stratified according to absence/presence of a documented diagnosis of Primary Sjögren's Syndrome.

The study was ongoing at the time of amendment and at the beginning of September 135 patients had already been randomized. The randomization list generated on March 22, 2019 will be stopped when the last randomization number used will be at the end of a block. Moving forward, the replacement list will be used. According to the amendment n° 1, the replacement randomization schedule will be stratified according to absence/presence of a documented diagnosis of Primary Sjögren's Syndrome.

Each randomized patient after amendment will be allocated with randomization number, according to the stratified randomization list using an Interactive Web Response System (IWRS). Drop outs after randomization will not be replaced.

Randomization lists as well as associated kit numbers will be generated by a member of Syneos Health Biostatistics department, not involved in the conduct of the study.

Patients will be assigned to treatment in numerical order. A tear-off label from the kit box, with the kit number, will be attached to the investigational product dispensing log.

The enrollment of patients will be scheduled in order to assure an inclusion of approximately 240 patients without Primary Sjögren's Syndrome diagnosis and at least 60 patients with Primary Sjögren's Syndrome.

For patients already enrolled in the study, the assignment to a strata will be based on Medical history form (see section 8.1).

The identity of the treatments will remain unknown to the patient, Investigator, site staff and Sponsor's clinical research personnel until the study is unmasked for the final statistical analysis (after data base lock) except in case of specific events that will require unmasking of the patient.

The vials containing rhNGF (20 µg/mL) or vehicle will be identical in appearance, and the contents of the vials will be indistinguishable. All staff directly involved in the analysis of study results will remain masked to treatment assignments while the study is in progress.

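### Early patients whose history says only 'Sjogren' are counted as Absence of Primary Sjögren, which may shrink the Presence stratum in the exploratory analyses

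*SAP*

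**What the plan says.** SAP 8.1 states: "For patients already enrolled in the study, the assignment to a strata will be based on Medical history form". An entry of 'Primary Sjogren' puts the patient in Presence. For the unqualified word the rule is that, if only 'Sjogren' "is recorded then the patient will be assigned to" Absence, and the remainder are covered by "In all other cases, the patient will be assigned to 'Absence of Primary Sjogren".

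SAP 3.5 gives the number exposed: "at the beginning of September 135 patients had already been randomized". The unstratified list was to run on to the end of a block, so 135 is a minimum. SAP section 2 gives the final size: "The study stopped to 261 patients instead of 300 originally planned".

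Later patients are stratified at randomization on a documented diagnosis (Protocol 4.5, SAP 3.5). Inclusion criterion 9, new in protocol version 2.0, defines the standard: patients "must meet either 4 out of 6 total criteria OR 3 out of 4 signs" (SAP 3.3.1; Protocol Appendix 3).

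The stratum is used in:
- the exploratory interaction model for Schirmer I, tested at 0.10 (SAP 8.1);
- the same model for SANDE, Schirmer II, staining and TFBUT (SAP 8.2);
- the efficacy and safety summaries by stratum (SAP 6.6, section 8 and 9.3);
- patient disposition (SAP 7.1).

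Neither document plans a site query for unqualified entries, or an analysis that reclassifies or excludes them. SAP section 11 does not list the rule among the changes from the protocol.

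**The concern.** One variable is built from two standards. After the amendment, Presence means a documented diagnosis against named criteria. Before it, Presence means that a particular word was recorded. Two patients with the same disease can be placed in different strata because of enrolment date and wording.

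An unqualified 'Sjogren' entry does not show that Primary Sjögren is absent; it leaves the type open. Protocol section 4 expects that such patients may already have been enrolled, so the case is foreseeable.

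The exploratory look at Primary Sjögren is a stated study aim (Protocol 3.1, SAP 3.1), and the amendment set a minimum of 60 such patients to make it informative. If true cases sit in Absence, Presence is smaller and its estimates less precise. An apparent shortfall against 60, or a null interaction, could then partly reflect how histories were written.

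**Working it through.** **The plan's own figures.** The plan gives no count of unqualified entries. Its sample size reproduces: 2 × [10.78 × (1.960 + 1.282) / 5.3]² = 86.9, so 87 per group at one-sided 0.025 and 90% power. With 76 per group the power is 85.8%, against the stated minimum of 85%. Neither figure involves the stratum, because the primary model contains treatment only (SAP 8.1). Nothing below changes them.

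**Exposure to the rule.** 135/261 = 51.7%. The other 126 patients are taken as stratified at randomization.

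**Inputs.**
- Prevalence p of Primary Sjögren: 20% from the planned minimum (60/300), or 25% from NGF0216, for which Protocol 9.1 cites "a similar prevalence of patients with Primary" Sjögren's. Assumed equal before and after the amendment.
- Share f of early Primary Sjögren patients recorded without the word 'Primary': not given, so taken from 0 to 1.

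**Formulas.**
- Misplaced patients: m = 135 × p × f
- Presence stratum as analysed: 261p − m
- Share of Absence that is truly Primary Sjögren: c = m / [261(1 − p) + m]
- Stratum contrast retained: 1 − c. If Presence is pure, the expected effect in Absence is (1 − c) × (effect without Primary Sjögren) + c × (effect with it). The observed difference is therefore the true difference × (1 − c).

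**Results.** Early patients with Primary Sjögren: 135 × 0.20 = 27.0, or 135 × 0.25 = 33.75. In the whole trial: 261 × 0.20 = 52.2, or 261 × 0.25 = 65.25.

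| p | f | m | Presence analysed | Absence analysed | c | Contrast retained |
|---|---|---|---|---|---|---|
| 20% | 0 | 0 | 52.2 | 208.8 | 0% | 100% |
| 20% | 0.5 | 13.5 | 38.7 | 222.3 | 6.1% | 93.9% |
| 20% | 1 | 27.0 | 25.2 | 235.8 | 11.5% | 88.5% |
| 25% | 0 | 0 | 65.25 | 195.75 | 0% | 100% |
| 25% | 0.5 | 16.9 | 48.4 | 212.6 | 7.9% | 92.1% |
| 25% | 1 | 33.75 | 31.5 | 229.5 | 14.7% | 85.3% |

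The share of Presence lost is m / 261p = 0.517 × f, whatever p is: 26% at f = 0.5 and 52% at f = 1. With a similar SD in both strata, standard errors within Presence rise by the factor 1/√(1 − 0.517f). That is 1.16 at f = 0.5 and 1.44 at f = 1. Loss of precision is therefore the larger effect, and dilution of the contrast the smaller one.

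**The case against.** The rule can be defended on the stratum's own definition, a documented diagnosis of *primary* disease. A bare 'Sjogren' entry does not document that. Appendix 3 separates primary from secondary disease, and secondary patients belong in Absence. The rule is prespecified, does not depend on treatment, and favours a specific Presence stratum over a complete one. All of this stands. What it does not answer is that the type is left unknown for some early patients when existing records might settle it, and that no analysis tests the choice.

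The 25% figure describes Primary Sjögren taken from medical histories in the earlier study. Primary disease was evidently identifiable there, which weakens any assumption that the word was usually omitted. This also stands: f could be small, and zero misplaced patients cannot be excluded.

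Medical history is listed by patient (Listing 16.2.4.2), so a reader could find the entries. That gives visibility but does not correct the strata.

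Four stronger readings are tempting, and the documents do not support them:
- *Half the trial is misclassified.* The 52% is exposure to the rule only.
- *Every bare 'Sjogren' entry is an error.* Entries for secondary disease are correctly placed.
- *The error can run only towards Absence.* An early 'Primary Sjogren' entry goes to Presence with no stated check against Appendix 3, so false positives are possible too.
- *Sites were never prompted to write 'Primary'.* The earlier protocol's full text and the eCRF instructions are not available.

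**Conclusion.** The concern holds as a limited weakness in the exploratory Sjögren analyses. For at least 135 of 261 patients the stratum rests on wording that may not settle the disease type, and undetermined entries default to Absence.

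The number of true Primary Sjögren patients placed there is unknown: 0 to about 27 at 20% prevalence, 0 to about 34 at 25%. In the extreme case Presence loses 52% of its patients; the contrast between strata still keeps at least about 85% of its size. These figures assume equal prevalence before and after the amendment, a Presence stratum free of false positives, and misplaced patients who respond like other Primary Sjögren patients. If recruitment after the amendment raised the prevalence, the share lost is smaller.

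A reader might infer that the vehicle comparison or the main result is compromised. It is not: the arms are as randomized, and the primary Williams test, its alpha and its power do not involve the stratum. Only the exploratory interaction tests and the Presence/Absence efficacy and safety tables are affected. The change is worth making because it is cheap, but it is not critical to the trial's main conclusion.

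**What to change.** Before database lock and while masked, query the site for each pre-amendment patient with an unqualified Sjögren entry. Ask for existing source documentation of primary versus secondary disease, and set the stratum from the answer. The blind data review meeting already planned in SAP 5.6 and 6.3.1 is a natural point to close this.

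Full re-adjudication under Appendix 3 should not be required. The schedule of evaluations collects no biopsy, serology or salivary data, so some entries will stay unresolved. For those:
- keep the prespecified assignment to Absence in the main exploratory analysis and the stratum tables;
- repeat the interaction analysis with them counted as Presence;
- repeat it again with them excluded;
- report their number by arm.

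Add the revised rule to SAP 8.1 and record it in SAP section 11.

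The cost is a limited number of data queries, whose count the documents do not allow to be fixed in advance, and two repeats of an exploratory model. Sample size, the primary analysis and the main tables' patient counts overall do not change.

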8.2. Secondary Efficacy Endpoints and Analyses

The same exploratory sensitivity analysis will be also conducted for SANDE, Schirmer Test II, Corneal and Conjunctiva Vital Staining and TFBUT.

8.2.1. Change from baseline in Symptoms questionnaire (SANDE) scores for severity and frequency

The SANDE questionnaire is comprised of 2 questions at each visit:

- (1) How often do your eyes feel dry and/or irritated?
- (2) How severe do you feel your symptoms of dryness and/or irritation are?

One measure frequency of symptoms ranges from "0 mm = rarely" to "100 mm = all of the time," and the other measure severity of symptoms ranges from "0 mm = very mild" to "100 mm = very severe".

The global SANDE score will be calculated by multiplying the frequency score by the severity score and obtaining the square root [4].

Change from baseline at Week 4 will be analyzed using analysis of variance including treatment as factor followed by pre-planned comparisons from Vehicle and rhNGF dosages according to Williams' procedure.

Descriptive statistics (actual and change from baseline) of SANDE scores will be presented by treatment and visit. Comparison (descriptive in nature) of the change from baseline of each treatment versus placebo will be performed by means of a t-test at each timepoint.

This document is confidential.

Symptoms questionnaire (SANDE) scores will be also listed.

